### 6.3 Treatment schedule

Parameter	Pre-Study	SBRT			10-12 weeks post-treatment	Q 3 months until 24 months
		Fx 1	Fx 2	Fx3		
History	X	X		X	X	X
Physical exam	X	X		X	X	X
Measurement of disease	X				X	X
Performance Status	X				X	X
Serum Chemistry	X*				X ▲	X ▲
Hematologic Studies including CBC	X*				X	X ▲
CT Scan	X				X	X Ω
Serum or Urine Pregnancy Test for WOCBP	X					
Histologic and Morphologic Confirmation and Margin Status	X					
QOL assessment	X				X	X

\* Within 30 days of study start

▲If clinically indicated

ΩMay be modified by oncology team if patient receives system therapy

### 6.4 Post-treatment evaluation and plan

#### 6.4.1 Evaluation of CT Imaging

A follow-up CT scan will be obtained at 10-12 weeks post-SBRT and then every 3 months until end of study. If the patient goes on to receive systemic therapy, the follow-up CT schedule can be modified at the discretion of the oncology team.

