## 4.0 SUBJECT SELECTION AND ELIGIBILITY

### 4.1 Selection of subjects

Enrollment is defined as the first day of protocol therapy.

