#### *5.3 On-Treatment assessment and post-treatment toxicity evaluation*

All subjects will be seen prior to delivery of each fraction of SBRT with toxicity evaluated by physical examination. Subsequently, subjects will be evaluated for toxicity 10-12 weeks later and then every 3 months until at least 2 years. Toxicities will be scored by the NCI CTC AE version 4.0. Also see Section 6.0.

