### 6.2 Evaluation during treatment

The subjects will be carefully followed while on active treatment and post-treatment for 24 months, or until death. Evaluation during treatment will consist of the following activities:

- 6.2.1 Administration of SBRT
- 6.2.3 Interim medical history and physical examination at baseline, prior to SBRT treatment, at the end of SBRT, and 10-12 weeks after SBRT then every 3 months thereafter for up to 24 months.
- 6.2.4 Serum chemistry and electrolytes to include BUN, creatinine, sodium, potassium, bicarbonate, chloride, calcium, magnesium, glucose, total bilirubin, AST, ALT, alkaline phosphatase post-treatment as clinically indicated
- 6.2.5 Hematologic studies to include CBC with differential and platelet count prior to SBRT and repeated 10-12 weeks later and then at follow-up as clinically indicated.
- 6.2.6 CT scan will be obtained at 10-12 weeks post-treatment and will be reviewed for evidence of response. Since these subjects will likely have no gross disease on imaging, the main goal of the follow-up scans is to monitor for local and distant progression as defined below.

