#### 6.4.2. Definition Local Progression Free Survival

In this study, LPFS is defined as the time from enrollment to first documentation of progressive disease (PD) in the target lesion. Death or development of distant disease is not regarded as an event. For patients that undergo surgical resection, local progression will be defined as disease recurrence detected on follow-up imaging (CT or FDG-PET/CT) that is located within the SBRT target volume.

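### CT follow-up may be changed without limit once a patient is on systemic therapy; if scans drift to 6-monthly, 2-year LPFS is overstated by about 3 to 5.7 points, against under 1 point on the default schedule

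*Combined protocol and SAP*

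**What the plan says.** - **Default schedule.** Section 6.4.1: "A follow-up CT scan will be obtained at 10-12 weeks post-SBRT and then every 3 months until end of study". The table in Section 6.3 heads the same column "Q 3 months until 24 months".
- **Exception.** Section 6.4.1: "If the patient goes on to receive systemic therapy, the follow-up CT schedule can be modified at the discretion of the oncology team". A footnote to the 3-monthly CT cell in Section 6.3 repeats it. No minimum interval, visit window or fixed landmark scan is given. Section 3.5 leaves systemic therapy to the medical oncologist and does not say how many patients will receive it.
- **Endpoint.** Section 6.4.2: "LPFS is defined as the time from enrollment to first documentation of progressive disease (PD) in the target lesion". For resected patients, who are the whole population here, the event is "disease recurrence detected on follow-up imaging (CT or FDG-PET/CT) that is located within the SBRT target volume". Death does not count as an event.
- **Time origin.** Section 4.1: "Enrollment is defined as the first day of protocol therapy".
- **End of follow-up.** Section 5.3 (toxicity): "subjects will be evaluated for toxicity 10-12 weeks later and then every 3 months until at least 2 years". Section 6.2: "post-treatment for 24 months, or until death".
- **Analysis.** Section 7.3.3 plans Kaplan-Meier curves and a 2-year LPFS estimate with a 95% confidence interval. It gives no rule for interval censoring and no censoring date for patients without an event. Section 7.2.1 rests the sample size on a one-sided log-rank test at 0.05, 40% against 60%.

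**The concern.** A local recurrence enters the data only when a scan shows it, and it carries the date of that scan. Wider spacing therefore moves events later, and some move past month 24 or are never recorded. Both raise the LPFS estimate, which is the direction that favours SBRT. The exception may reach many patients: Section 1.3 calls early systemic chemotherapy important, and Section 1.3.1 makes earlier systemic therapy an aim. The size of the error then depends on scheduling decisions that the plan does not bound and the analysis does not correct.

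**Working it through.** **1. The plan's own figure.** Take exponential LPFS with h0 = −ln 0.4/24 and h1 = −ln 0.6/24 (hazard ratio 0.557), 50 patients, 24 months of accrual plus 24 of follow-up, and a one-sample log-rank statistic (E − O)/√E compared with 1.645. Expected events are 26.5 under 60% and 36.9 under 40%. Simulation gives 94.2% power, matching the stated 94%, and about 4% type I error with exact event times.

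**2. Last default scan.** Ten to twelve weeks is 2.30 to 2.76 months. Three fractions on alternate days add about 0.13 to 0.23 months, so the first scan falls 2.43 to 2.99 months from enrollment. Seven 3-month steps (21 months) put the last scan by month 24 at 23.4 to 24.0 months.

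**3. Bias in the 2-year estimate.** If patients without a recorded event stay at risk to month 24, the Kaplan-Meier value at 24 equals the true S at the last scan by then. Bias = S(t_last) − S(24), with S(t) = S(24)^(t/24).

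| Last scan (months) | True 40% reads as | True 60% reads as |
|---|---|---|
| 23.5 (default) | 0.4^(23.5/24) = 40.8% | 60.6% |
| 22.5 (4-monthly, assumed) | 42.4% | 61.9% |
| 20.5 (6-monthly, assumed) | 0.4^(20.5/24) = 45.7% | 64.6% |

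Over the whole default range in step 2, the bias is 0.0 to 0.9 points at 40% and 0.0 to 0.7 at 60%.

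**4. Only some patients affected** (true 40%, the rest on the default schedule). At a 50% share: 0.5 × 45.7 + 0.5 × 40.8 = 43.2%, or +3.2 points. At 30% the bias is +2.3, at 70% +4.2, at 90% +5.2.

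**5. Check by simulation** (n = 50, median OS 20 months assumed; adjuvant-treatment medians cited in Sections 1.2 and 1.3 run from about 16 to 25). With censoring at death or month 24, the mean estimates are about 41% on the default schedule, 43.3% with half on 6-monthly scans and 45.7% with all. With 6-monthly scans about 15% of local failures occurring before death or month 24 are never recorded, against 6% on the default schedule.

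**6. Effect of the censoring rule on log-rank type I error.**

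| Scans | Censored at death or month 24 | Censored at last scan |
|---|---|---|
| 3-monthly | 10.2% | 6.3% with deaths, 6.8% without |
| 6-monthly | 25.4% | 7.6% with deaths, 9.6% without |

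The first rule counts time after the last scan, when no event can be found, and so inflates E. The rule also affects the estimate: with half the patients on 6-monthly scans, last-scan censoring gives 40.5% instead of 43.3%. With all patients on them it does not help, because nobody is at risk after 20.5 months and the curve stays near 45.7%.

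**7. Effect of a late closing scan.** If the 23.5-month scan moves to 24.5, ordinary Kaplan-Meier dates its events after month 24. The last informative scan is then 20.5 months and the estimate is again about 45.7%, on a schedule that is otherwise 3-monthly.

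**The case against.** The strongest reply is that the default plan is sound to within a point and that the rest is hypothetical. Much of this stands.

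- A reader might infer that a last scheduled scan before month 24 is itself worth several points. The documents do not support that: it is worth 0.0 to 0.9. Nor is the end of scanning settled, since Section 6.4.1 runs to the end of the study.
- Systemic therapy is optional, no modified interval is stated, and a modification could mean closer scanning. Section 6.3 keeps history, examination and disease measurement 3-monthly without the footnote, and FDG-PET/CT also counts, so visits may prompt imaging. These points limit how likely a large bias is. They do not set a floor on scan frequency.
- A reader might quote 25% as the plan's false-positive risk. That figure needs 6-monthly scans in every patient and one particular censoring rule that the plan does not state.
- A reader might blame failures that go unseen before death. They do occur, but they do not drive the bias in the 2-year estimate: with deaths switched off it is essentially unchanged.
- A reader might conclude that the comparison with 40% is biased towards success. Section 7.2.1 takes 40% from the investigators' experience with no imaging schedule stated. If those failures were also dated at detection, some of the bias cancels.
- It cannot be said that the decision lies outside the study team, because the oncology team is not defined.

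What remains is an unbounded permission acting on the assessment that defines the primary endpoint, with no safeguard in the analysis.

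**Conclusion.** The concern holds as a gap in the plan, of moderate size and conditional on practice. The direction is upward whenever scans are stretched. At a true 40%, the overstatement is under 1 point on the default schedule, about 3 points if half of patients move to 6-monthly scans, and at most about 5.7 points if all do. These figures assume exponential times, a first scan at 2.5 months, no other imaging, and censoring at death or month 24. The type I error of the design test cannot be stated without a censoring rule. The net effect on the comparison with 40% cannot be determined from the documents. The change is worth making because it is cheap and removes the dependence on these unknowns.

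**What to change.** 1. **Sections 6.3 and 6.4.1.** Exempt the landmark scan from the modification clause. Place it in a window that closes at month 24 from enrollment for every patient still at risk, or assign scans within a stated window to the month-24 visit. Measure the window from enrollment: Section 6.2 counts from treatment, so a scan at 24 months after treatment would fall just past the landmark. Extra clinically driven scans remain allowed.
2. **Sections 5.3, 6.3 and 6.4.1.** Reconcile when scanning ends.
3. **Section 7.3.3.** Estimate 2-year LPFS with an interval-censored method (last negative to first positive scan), with patients without an event censored at their last negative scan. This must be the primary estimate if the closing scan may fall after month 24. Otherwise it should be at least a named sensitivity analysis.

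The scan and the analysis are both needed. Adding back the 23.5-month scan to an otherwise 6-monthly schedule returns the estimate to 40.7%, but leaves log-rank type I error at 17.5% with censoring at death or month 24. Conversely, no analysis can recover month 24 without assumptions if nobody is scanned near it.

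The cost is protocol and SAP wording, slightly less scheduling freedom for one scan already in the schedule, and a little more analysis.

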#### 6.4.2. Definition Local Progression Free Survival

In this study, LPFS is defined as the time from enrollment to first documentation of progressive disease (PD) in the target lesion. Death or development of distant disease is not regarded as an event. For patients that undergo surgical resection, local progression will be defined as disease recurrence detected on follow-up imaging (CT or FDG-PET/CT) that is located within the SBRT target volume.

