#### 3.2 Radiation simulation

Contrast-enhanced CT based simulation will be obtained prior to any adjuvant treatment (2-4 weeks post-op depending on healing). The target volume will be identified based on fiducial marker placement at time of surgery as well as a detailed discussion and image review with the operating surgeon. This area will be contoured on axial CT images obtained at 1.25 mm slice thickness. These volumes will then be reconstructed into a 3-dimensional image set for SBRT planning. Subjects will be simulated in the treatment position (supine with arms raised) on the CT scanner table the appropriate immobilization. Optiray® contrast (125 mL Optiray 350; 350 mg/mL organically bound iodine; Ioversol; Mallinckrodt Inc., St. Louis, MO, USA) will be administered intravenously at a flow rate of 2.5 mL/s. A helical CT scan of the abdomen will be acquired with intravenous contrast starting 30 seconds prior to CT acquisition.

A 4D CT data acquisition for the same axial extent will be obtained. The images will then be electronically transferred from the CT workstation via DICOM3 to the appropriate treatment planning workstation in the department of radiation oncology. Based on axial CT images, fiducial marker placement, review of the pathology report, and a detailed discussion with the operating surgeon, contours will be drawn of the clinical target volume (CTV), which is defined as the area at risk for microscopic disease. The planning target volume (PTV) will be equivalent to the CTV unless motion is detected on the 4D motion study. If there is motion, the amount of motion in the superior-inferior, lateral, and anterior-posterior directions will be the margin given. Surrounding normal and critical structures will also be contoured by the treating radiation oncologist including the kidneys, liver, small bowel, spinal cord, and stomach if necessary.

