#### 4.1.1 Number of subjects

50 patients will be enrolled to the study. The study has been designed to detect a 20% improvement in the rate of local progression-free response over that of historical controls.

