### 7.2 Sample Size and Accrual Rate

#### 7.2.1 Sample Size

From the Investigators' treatment experience, the 2-year local progression-free survival rate for the standard of care is 40%. This phase II study aims to improve it to 60% with SBRT. We plan to have 24 months of accrual, and 24 months of follow-up beyond the last patient enrolled on study. Under assumption of exponential survival, a total of 50 patients will provide 94% power to detect a statistically significant improvement in survival by one-sided log-rank test at significance level 0.05. Assuming that there will be no loss to follow up and no ineligible case, a total of 50 patients will be accrued for this trial.

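### The primary LPFS event counts only recurrence inside the SBRT target volume, and the 40% benchmark is not shown to have been scored over a comparable region

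*Combined protocol and SAP*

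**What the plan says.** Section 6.4.2 defines the primary event for resected patients: "local progression will be defined as disease recurrence detected on follow-up imaging (CT or FDG-PET/CT) that is located within the SBRT target volume". Section 4.1.2 admits only resected patients, so this rule governs the whole primary endpoint. The same section adds: "Death or development of distant disease is not regarded as an event".

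The target is drawn patient by patient. Section 3.2 bases the CTV on CT, fiducial markers, pathology and discussion with the surgeon, and describes it as the area "which is defined as the area at risk for microscopic disease". On the margin around it, the section says: "The planning target volume (PTV) will be equivalent to the CTV unless motion is detected on the 4D motion study".

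The reference rate is in section 7.2.1. From the investigators' experience, "the 2-year local progression-free survival rate for the standard of care is 40" per cent, and "This phase II study aims to improve it to 60% with SBRT". Section 4.1.1 describes the aim as to "detect a 20% improvement in the rate of local progression-free response over that of historical controls". Neither section says which patients gave the 40%, how many there were, or what counted as a local failure in them.

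Two other places bear on this. Section 6.4.3 counts progression for TTP only in the target volume or at a distant site. The Protocol Summary lists locoregional and distant control among the efficacy data, but section 6.4 does not define it and section 7.3.3 does not name it.

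**The concern.** With no concurrent control arm, the efficacy reading rests on 60% and 40% being rates of the same event. The trial's event is tied to a volume that exists because the patient had SBRT. The benchmark is presented as a rate without SBRT, so the section 6.4.2 definition cannot be applied to those patients directly. Some equivalent region would have to be reconstructed, and no such step is reported.

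The direction of any mismatch is clear. If the benchmark counted recurrence over a wider area, some failures that lowered the 40% would not count in the trial, and apparent LPFS would rise whatever SBRT does.

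The plan also lacks a second endpoint that would show this. A recurrence in the resection bed but outside the target is not an LPFS event and, unless it is classed as distant, not a TTP event either. Recurrence at the edge of the target, which matters when the PTV may equal the CTV, could go unreported.

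**Working it through.** **Inputs from section 7.2.1:** N = 50; 24 months of accrual and 24 months of further follow-up; exponential times; no loss; one-sided log-rank test at 0.05; 40% against 60% at 2 years.

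**Step 1: reproduce the plan's power.**
- Null hazard: λ0 = −ln(0.40)/24 = 0.0382 per month.
- Alternative hazard: λ1 = −ln(0.60)/24 = 0.0213 per month.
- Hazard ratio: ln(0.60)/ln(0.40) = 0.5575.
- Expected events under 60%: 50 × [1 − (0.60 − 0.36)/0.5108] = 26.5.
- One-sample log-rank test: Z = (E − O)/√E, positive if Z > 1.645. Here O is the observed number of events and E is λ0 times total follow-up.
- Simulation with uniform accrual gives 94% power, as stated, and an actual type I error of about 4%. The plan's arithmetic is sound, provided that both rates count the same event.

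**Step 2: an inert treatment with a narrower event.** Let f be the share of the benchmark's local-failure hazard that lies inside the SBRT target. This is an assumption, because the documents give no value. With no SBRT effect, the in-target hazard is f × λ0 and the apparent 2-year LPFS is 0.40^f.

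By hand for f = 0.8:
- LPFS = 0.40^0.8 = 48.0%.
- Hazard over 24 months = 0.8 × 0.9163 = 0.733.
- Expected O = 50 × [1 − (0.480 − 0.231)/0.733] = 33.0.
- E = 33.0/0.8 = 41.2.
- Mean Z ≈ (41.2 − 33.0)/√41.2 = 1.28.
- Chance of exceeding 1.645 ≈ Φ(1.28 − 1.645) ≈ 36%. Simulation gives about 35%.

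**Step 3: less favourable follow-up.** Section 6.4.2 makes death a non-event, so deaths censor, and the schedule in section 6.3 ends at 24 months. I repeated the simulation with each patient capped at 24 months, then with independent exponential death (median 20 months) added. The 20 months is an assumption; treated-group medians in the Background run from about 16 to 25 months.

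| f (assumed) | Apparent 2-year LPFS, no SBRT effect | Positive test, plan's assumptions | 24-month cap | Cap and deaths |
|---|---|---|---|---|
| 1.0 | 40% | 4% | 4% | 4% |
| 0.9 | 44% | 14% | 12% | 10–11% |
| 0.8 | 48% | 35% | 30% | 23% |
| 0.7 | 53% | 64% | 55% | 42% |

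The apparent rate would reach 60% only at f = 0.5575, the hazard ratio from step 1, where the test is positive 94% of the time under the plan's assumptions.

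**The case against.** A reader might infer that the 40% cannot have been scored in the same way. The documents do not go that far. They do not describe the benchmark cohort. Section 1.2 says chemoradiation was long considered standard after resection, so benchmark patients may have had a radiation field in which recurrence could be scored. Section 5.3.4 says surgeons at the site routinely mark at-risk margins with fiducials, so a comparable region might be reconstructed. What stands is that comparability is not shown.

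A reader might also infer that the target is small and leaves out much of the bed. No volume is given, and section 5.1 speaks of treating the primary site together with areas of possible occult spread. The size of any bias depends on that unknown share.

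The far end of the range, where an inert treatment reaches 60%, sits badly with the site's own 24 post-operative SBRT patients (section 1.3.1). Their 1-year freedom from local progression was 66%, or about 0.66² = 44% at 2 years if exponential. If those patients were scored in-target, an inert treatment at f near 0.56 would outperform SBRT as actually observed. The check is rough: the scoring region is not stated, and 95% at 6 months with 66% at 1 year does not fit an exponential curve (0.95² = 90%). It still argues against resting the point on the extreme scenarios.

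Section 7.3.3 plans a Kaplan-Meier estimate with a 95% confidence interval and no test against 40%; the log-rank test appears only in section 7.2.1. That limits the formal error-rate argument. But the study is sized and described as detecting a gain over historical controls, and the estimate carries the same bias when read against 40%.

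Finally, in-target control is a reasonable measure for a local treatment. The difficulty lies in the comparison, not in reporting it.

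**Conclusion.** The point holds as a gap in comparability, and should be fixed. The primary event is confined to the SBRT target, while the benchmark has no stated source or local-failure region. If the benchmark region was wider, even a modest mismatch matters. With 10% to 30% of benchmark local failures outside the target, an inert treatment would show 44% to 53% at 2 years. The nominal 5% test would be positive about 14% to 64% of the time on the plan's assumptions, or about 10% to 42% with deaths and a 24-month cap.

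These are scenarios. They rest on an undocumented f, exponential times and, for the lower set, an assumed 20-month median survival independent of local recurrence. The documents do not establish that the benchmark was scored differently, or that the whole 20-point gain could be an artefact.

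**What to change.** - **Record the site.** From the CTs already planned, classify each local recurrence as in-target, at the target margin, or elsewhere in the resection bed.
- **Section 6.4.2.** Define LPFS over the resection bed, including the target, and use that version for any comparison with 40%.
- **Section 7.3.3.** Report in-target LPFS alongside it as an estimate with its 95% confidence interval. Do not compare it with 40% unless the benchmark is shown to have been scored in an equivalent region.
- **Section 7.2.1.** State the source of the 40% and the region in which local failure was counted.

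The cost is protocol wording, one case-report field and some work on the benchmark's origin; no extra patients or scans are needed. The bed-level LPFS will be somewhat lower than the in-target figure. The benchmark's region may need checking or may not be recoverable; if it is not, the comparison with 40% should be labelled descriptive.
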